Once potential participants are identified, introduction letters will be mailed to their addresses. Approximately after two weeks of mailing the introduction letter to Veterans, research staff will contact potential participants to inform them about the study, obtain verbal consent for and conduct initial screenings over the phone. For Veterans who contact us over the phone or in-person, (e.g., after reading a posted flyer), we will obtain verbal consent for and conduct initial screenings in person or over the phone.

If a Veteran is screened as eligible to participate in the study, a date and time will be scheduled for the Veteran to come into one of the three study sites (East Orange VA, Canandaigua VA or Bedford VA) to be consented into the study and complete the baseline questionnaires and neuropsychological assessments.

b. Sessions

Once consented and baseline assessments (described below) are completed, therapy sessions will be scheduled with a Study Provider from the East Orange VA. Study providers will be a licensed provider, e.g., psychologist, nurse, social worker, or a trainee e.g., working under a licensed provider, at the East Orange VA. A Study Provider from the East Orange VA will provide the sessions via phone with all participants from all VA sites (East Orange VA, Canandaigua VA, and Bedford VA). We will have a standardized assessment regimen that all Study Providers will adhere to. Therapy sessions will be scheduled weekly, and may be adjusted to accommodate the Veteran's schedule and/or needs.

The telephone sessions with the Study Provider will generally be 1 hour. Most telephone sessions will be voice recorded and transcribed for quality assurance, i.e., fidelity to study protocols, length of sessions, engagement of participants. Coding of telephone sessions will occur by our off site collaborators once proper approvals are in place (i.e., DUA).

Study Arms

Veterans will be randomized either to the PST (treatment) or Health Education group (control).

If randomized to the PST (treatment):

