We will make a concerted effort to contact participants for their appointments and assessments through phone calls and letters. We will not reach out to Veterans who do not wish to continue in the study.

Consent Procedures

Informed consent is an ongoing process. At the phone screening, Veterans will provide a verbal consent. At the baseline assessment, when the Veteran is considering enrolling in the study, information will be presented in-person to enable the Veteran to voluntarily decide whether or not to participate as a research participant. The Investigator, study coordinator or research assistant will review and explain the study's purpose, experimental procedures, alternatives, risks, benefits and duration of the study in terms that the potential participant can understand. The Investigator or study team member will be available to address any concerns and answer any questions the Veteran might have regarding the study and the informed consent. After all questions have been answered and concerns addressed, the Veteran may sign the Consent Form. A signed copy will be provided to the Veteran and the original copy will be placed in the Veteran's study folder and scanned into his/her CPRS record.

Participant Compensation

Participants may receive a total of \$200 for their participation in the study as follows: \$30 for completion of the baseline assessments; \$70 for completion of the 12th session questionnaires and neuropsychological assessments. We will contact participants after the 4th session and also at 6 months post-treatment to complete written questionnaires – participants will receive \$50 for completing each of these questionnaires. For compensation, participants will complete and sign a voucher, and a check will be mailed within 6-8 weeks. If the subject does not want to continue

in the study, s/he may come to an assessment site and complete a study exit visit and assessment; they will still receive \$70.

Our budget includes funds to pay for participant travel as needed.

c. Assessment Methods

In this section we summarize all of the assessment instruments/procedures used to determine eligibility, assess neuropsychological functioning, and disability.

Table 2 outlines the study procedures that are described below: assessments, mailed questionnaires, qualitative interviews, and therapy sessions with the study provider.

		Weeks												Months
	Baseline	1	2	3	4	5	6	7	8	9	10	11	12	6
Questionnaires	X				X								X	X

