Neuropsychological Assessments	X												X	
Qualitative Phone Interview	X												X	

Baseline and 12th Week Assessments

Baseline and 12th week assessments will be conducted in-person at any one of the study sites: East Orange VA, Canandaigua VA or Bedford VA. The baseline and 12th session assessments include completing written questionnaires and participating in neuropsychological assessments.

If the need arises (e.g., from fatigue) during the baseline or after the 12th session assessment, participants may have the option to complete the questionnaires at home and return them via mail in a prepaid envelope or complete the questionnaires via phone at a time and date that is convenient for him/her.

Participants may be provided the option of completing the written questionnaires and qualitative assessments only – and not completing the neuropsychological assessments. Questionnaire packets will still be mailed to them to complete and return to us in prepaid envelopes. Questionnaires may also be completed via phone with a study staff member at a time and date that is convenient for the participant. In addition, participants may be offered the opportunity to travel into one of the three study sites to complete the in-person baseline and 12th week assessments. We have budgeted this cost into the grant proposal.

Special considerations for the Baseline Assessment only

The baseline only will include full consenting into the study. Participants will also be asked to complete a mental health provider form as part of their baseline assessment. They will be encouraged to talk to their mental health provider and this provider form will be used to document it.

We will obtain the names of participants' primary care providers (PCP) from their medical records or form they will complete. We are asking for this information so we may inform PCPs

of their patients' participation in the study. This will enable a PCP to notify us of any health concerns s/he may have about his/her patient's participation in the study. At the PI's and/or Study Provider's discretion, we may also contact participants' health care providers at any time during the study if we have a concern about the Veteran's health and/or safety.

4th week and 6th month Assessment

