We will mail or provide written questionnaires to all participants before or after the 4th session and also before or after 6 months post-treatment (see Table 1). All questionnaires will also be returned to the East Orange VA. Participants who wish, may also complete the questionnaires over the phone with a study staff member at a date/time that is convenient for the participant.

Qualitative Interviews

Participants may be asked to participate in 2 qualitative interviews. The qualitative interview will be conducted via phone by a study staff member from one of the sites at a date/time convenient for the participant after the baseline assessment and after the 12th session assessment. Participants will be asked about their perceptions of GWI and intervention methods. The qualitative interviews will be recorded using either a digital recording device or recorded directly onto a VA computer. Upon completion of all interviews, the recordings will be transferred to the secure shared network folder. The qualitative interviews will also allow us to modify the treatment in the future.

Assessment Instruments

a. Screening

The screening questionnaires will be used to determine inclusion and exclusion criteria. These questionnaires will be administered over the phone to determine a potential participant's eligibility, given exclusion and inclusion criteria, to enroll into the study. In addition to the listed questions we will ask potential participants about exclusionary medical and psychiatric conditions.

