These six life tasks reflect two underlying constructs: Activity limitations and Participation deficits. The WHO-DAS 2.0 is based off of the International Classification of Functioning, Disability and Health (ICIDH-2), which categorizes disability into three categories: physiological, activities and participation. The WHO-DAS 2.0 has been translated into 15 languages and tested in 13 countries. The six domains have a factor loading of 0.82 to 0.98 and all load onto the general disability factor. Participants will be asked to complete this at all time points. We will use the WHO-DAS 2.0 screener which is a 12 item measure at screening. The WHO-DAS 2.0 screener explains 86% of the variance in the full measure and will reduce burden at screening. As the WHO-DAS is the primary outcome measure, we will use the full, and more valid, 36 item measure during the study.

3. Columbia-Suicide Severity Rating Scale (C-SSRS): The C-SSRS is the gold standard for suicide assessment. It is used by the VAs Center of Excellence for Suicide Prevention. The C-SSRS was developed by Columbia University and is used extensively across primary care, clinical practice, surveillance, research, and institutional settings. The C-SSRS in one study showed 100% sensitivity and specificity in identifying individuals who attempted suicide. Across three major randomized controlled trials, the C-SSRS demonstrated convergent, divergent, and predictive validity; sensitivity to change; sensitivity and specificity of the instrument; and internal consistency of the intensity subscale. (Posner et al., 2011) is part of a national and international public health initiative involving the assessment of suicidality, including general medical and psychiatric emergency departments, behavioral health organizations, medical homes, community mental health agencies, primary care, clergy, hospices, schools, college campuses, US Army, National Guard, VAs, Navy and Air Force settings, frontline responders, substance abuse treatment centers, prisons, juvenile justice systems, and judges to reduce unnecessary hospitalizations. At the screening and 12th session visit, this questionnaire will be administered by a member of the research staff.

b. Questionnaires

The questionnaires described by construct below will be administered at certain time points. Questionnaires may be administered in person at baseline and after the 12th session.

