Qualitative assessments and interviews may be recorded, transcribed, and coded for further data analyses. Personal identifiers will not generally be transcribed from the voice recordings.

Additionally, we will review participants' medical records and collect information on previous and future medical treatment including physical and mental health treatment, diagnoses and medication.

c. Neuropsychological Measures

These measures capture Problem-solving Ability or Executive Function. These measures will be administered in-person at the baseline assessment visit and after the 12th session assessment visit. Problem-solving, an executive function refers to the ability of an individual experiencing an undesirable situation to move to a more desirable one when no response is immediately apparent or available. Problem-solving is considered the most complex of all cognitive functions as it requires the use and integration of other cognitive functions like attention, processing speed, effort, and impulse control as well as other executive functioning skills like mental flexibility and abstract thinking. Neuropsychological testing can be used to measure participants' functioning in the entire range of cognitive skills that problem-solving demands. We propose to use 5 neuropsychological instruments to measure functioning in the following cognitive areas: Attention, processing speed, impulse control, effort, mental flexibility and abstract thinking.

1. Halstead Category Test, Russell Revised Version: The Category Test is an objective test of problem-solving ability, specifically abstract thinking and mental flexibility. The test takes 30-40 minutes to administer. Our previous work has shown that the Category Test is able to differentiate Veterans with GWI from Gulf War Veterans without GWI. The Category Test has acceptable test-retest reliability and has been used as an outcome in cognitive rehabilitation treatments.
2. The Conner's Continuous Performance Test-3 (CPT-3): The CPT-3 is a measure of ability to alternate attention, inhibit impulses and mental flexibility. The CPT-3 is a valid and reliable measure that and this version includes norms for adults with brain disorders as well as attentional disorders. It can and has been used in treatment efficacy trials.

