Data analyses will be conducted both on-site by study investigators and with proper approvals, including DUAs, at our affiliate institutes by current and future study investigators. All analyses will be primarily performed on an intention-to-treat basis. The statistical significance will be defined by a p value < 0.05 , unless specified otherwise. Calculations of the means, standard deviations, proportions, histograms, etc., will be conducted to explore the distributions of the data, identify outliers, and calculate correlations between variables. We will also determine confounders that need to be controlled for in our analyses. We will particularly examine if we need to control for depression measured with the PHQ-8 or PTSD symptoms measured with the PCL based characteristics that exhibit differences at the baseline (pre-intervention).

Due to repeated measures, we will analyze the data using mixed model analysis, with participants nested within therapists modeled by random effects. To address H1, disability (WHODAS II scores) will be treated as the dependent variable, and treatment assignment [PST vs. Health education], time [pre- vs. post-intervention] and their interaction will be modeled as fixed effects. Differences in the improvement of disability between Problem-solving therapy and Health education will be evaluated by the treatment by time interaction. Linear contrasts will be constructed to evaluate the improvement in disability for each treatment separately. Variables such as age, gender, education and the confounders identified in the preliminary analysis will be controlled as covariates in the statistical analyses. Data transformations (e.g., square root, log,

etc.) will be used to normalize data where necessary. The same mixed model analysis strategy will be applied to address H2a, H2b, H3a and H3b. We will also explore, using this same mixed model strategy, the impact of PST therapy on each of the four individual neuropsychological tests scored as a composite and scored individually (Category Test, CPT 3, Stroop Test, and TMT). We will use the same data analysis strategy to examine all secondary outcomes. These will be reported as secondary outcomes and will primarily be used to generate hypotheses.

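### The post assessment has two unreconciled anchors, session 12 and week 12, and the plan has no rule for outcomes of Veterans who stop sessions early

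*Combined protocol and SAP*

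**What the plan says.** **Session anchor.** Under Assessment Instruments, b. Questionnaires: "Questionnaires may be administered in person at baseline and after the 12th session". Under c. Neuropsychological Measures, the tests are "administered in-person at the baseline assessment visit and after the 12th session assessment visit". Participant Compensation, Qualitative Interviews, the C-SSRS entry and the data-safety section also refer to the 12th session.

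**Week anchor.** The section Baseline and 12th Week Assessments says "Baseline and 12th week assessments will be conducted in-person at any one of the study sites", and its next sentence switches to the 12th session. Table 2 and the Summary List of Measures and Timeline use weeks.

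**Pace.** Methods, b. Sessions: "Therapy sessions will be scheduled weekly, and may be adjusted to accommodate" the Veteran. Study Arms allows an additional session in either arm.

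**Other questionnaires.** "We will mail or provide written questionnaires to all participants before or after the 4th session and also before or after 6 months post-treatment". The Summary List heads these columns 4 week and 24 week (6 month).

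**Leaving.** Participant Compensation: a subject who does not want to continue in the study is told "s/he may come to an assessment site and complete a study exit visit and assessment", for the same $70 as the 12th-session assessment. Reducing Attrition: "We will not reach out to Veterans who do not wish to continue in the study".

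**Analysis.** Data Analysis, a. Data: "All analyses will be primarily performed on an intention-to-treat basis". The H1 model has time at two levels, before and after the intervention. Beyond the mixed model, no missing-data method or sensitivity analysis is given.

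**The concern.** An intention-to-treat comparison needs the outcome of everyone randomised, at a time that does not depend on how treatment went. Where staff follow the session-based text, WHO-DAS is measured whenever session 12 happens. A Veteran who never reaches session 12 then has no clear assessment date. Where staff follow Table 2, WHO-DAS is measured at week 12. Two sites could apply the protocol differently and both be compliant.

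The exit visit adds a third possible date. The analysis section does not say whether its score is a post value, a separate time point or unused.

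The plan also gives staff no instruction for a Veteran who wants no more sessions but has not left the study. If that person is treated as having left, outreach ends and the primary outcome is lost. At stake are the meaning of the post value in H1, some precision, and protection against bias if stopping or pace differs by arm.

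**Working it through.** The documents give no power calculation, SD, attendance rate or dropout rate, so there is no planned figure to reproduce. The numbers below show what the text permits under stated assumptions. They are not estimates of what will happen.

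**1. Do the two anchors agree?** Week of session 12 = 12 × weeks per session. Six months after treatment = that week + 26. The paces are assumed; the documents set no limit.

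| Weeks per session | Session 12 at week | With one added session | Six months after session 12, at week |
|---|---|---|---|
| 1 | 12 | 13 | 38 |
| 1.5 | 18 | 19.5 | 44 |
| 2 | 24 | 26 | 50 |

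The anchors coincide only in the first row without an added session. Even there, the text puts the last follow-up at week 38 and the Summary List at week 24, a gap of 14 weeks. If the Summary List column means 24 weeks after treatment, it falls at 12 + 24 = week 36, but the neighbouring 4 and 12 week columns appear to count from the start. At two weeks per session, session 12 falls on week 24 itself, so the post assessment and the Summary List follow-up would collide.

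**2. What if exit scores are coded as post values?** Assume the effect builds linearly from zero to its full size at week 12, and that a share q exits at week w in both arms. Effect retained = (1 − q) + q × w/12.
- q = 20%, w = 6: 0.80 + 0.20 × 0.5 = 0.90.
- q = 30%, w = 4: 0.70 + 0.30 × 0.333 = 0.80.

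This dilution needs no difference between arms.

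**3. What if stoppers are not followed?** Assume 300 randomised 1:1, two-sided 0.05, 80% power, pre–post correlation ρ = 0.5 and analysis of change. Detectable difference in SD units = 2.802 × √(2(1 − ρ) × 4/N).
- N = 300: 2.802 × √(4/300) = 0.32.
- N = 240 (20% lost): 2.802 × √(4/240) = 0.36.

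**4. Is there a bias between arms?** Suppose only those who finish are analysed, and stoppers' mean change is g SD worse than finishers' in both arms. Bias = g × (share stopping in PST − share stopping in health education).
- 20% against 20%: 0 for any g.
- 30% against 20%, g = 0.3 to 0.5: 0.03 to 0.05 SD. With 105 and 120 analysed, the type I error is 5.6% to 6.6%.

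In this illustration the bias is zero unless stopping differs by arm. The documents give no information on that.

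**The case against.** The strongest case against is that the plan contains most of what is needed. Table 2 and the Summary List give a calendar date. The questionnaires around session 4 and at six months go to all participants. Post questionnaires can be done by mail or phone. Staff are to make real efforts to reach participants for assessments as well as appointments. A mixed model can use incomplete records under missing at random. Assessment at the end of treatment is also a legitimate target, and fixing week 12 changes the question slightly.

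Much of this stands, and it rules out several stronger readings that a reader might infer:

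- *That the post assessment hangs only on session 12 or an exit visit.* A week-12 anchor also exists. The defect is that nothing says which one governs.
- *That outcome collection ends when sessions end.* The exit visit and the no-outreach sentence concern leaving the study. That they would reach someone who only stops sessions is an inference from silence.
- *That exit scores taken in the first weeks are pooled with week-12 scores.* No exit date and no coding rule appear anywhere.
- *That the arms will differ in pace or dropout.* The scheduling flexibility and the extra-session allowance cover both arms, and both have a workbook reviewed at each session. Attaching a bias to different attendance rates would need rates that the documents do not give.

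The objection does not supply the missing rules: which anchor governs, what window applies, how an exit score is used, and what happens to a Veteran who stops sessions and stays in the study.

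**Conclusion.** The point holds as an unreconciled anchor combined with missing follow-up rules, and it concerns the primary outcome. Outcome timing and missingness may depend on treatment received. A reader might go further and conclude that intention-to-treat cannot be delivered; the text supports only that it is not assured.

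The contradiction between six months after treatment and week 24 is in the documents and needs no assumption beyond weekly sessions. The other sizes are conditional: 80% to 90% of the effect retained under the exit-coding assumptions, and a detectable difference of 0.36 instead of 0.32 SD with 20% lost. The precision figure treats 300 as reached, although the protocol states it as a ceiling. It also overstates what a fix recovers, since Veterans who truly withdraw are lost either way. No difference between arms has been shown. This is a cheap improvement worth making, not a flaw that invalidates the design.

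**What to change.** 1. Schedule the 4-week, 12-week and 6-month questionnaires by weeks from randomisation, with a fixed window, whatever the number of sessions attended. Use the same terms throughout, and reconcile the two definitions of the 6-month follow-up.
2. Define stopping sessions separately from withdrawing from the study. State that Veterans who only stop sessions still receive the week-12 and 6-month questionnaires by the existing mail or phone routes.
3. Record the date of every assessment. Enter exit-visit scores at their actual time, not as the week-12 value. The H1 time factor then needs more than its two levels, which would also let the week-4 WHO-DAS, already collected, contribute.

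The cost is protocol wording plus some mailing and telephone work within existing procedures. Flexibility in scheduling sessions is untouched. The downside is that some week-12 questionnaires will be completed before session 12, so the comparison becomes one at a fixed time after randomisation rather than strictly at the end of treatment.

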Aim 1: To determine the impact of telephone delivered Problem-Solving Therapy on disability in GWV with GWI. H1: Among Veterans with GWI, telephone delivered Problem-Solving Therapy will produce greater improvement in disability as compared to telephone delivered health education.

Aim 2: To determine the effect of Problem-Solving Therapy on problem-solving ability in GWV with GWI. H2a & H2b: Among Veterans with GWI, telephone delivered Problem-Solving Therapy will produce greater improvement in (H2a) self-reported problem-solving ability (measured with the Problem-Solving Inventory) and (H2b) objective problem-solving ability (measured with a neuropsychological battery) as compared to telephone delivered health education.

H2c & H2d: Improvement in (H2c) self-report problem-solving ability and (H2d) objective problem-solving ability will mediate the effect of telephone delivered Problem Solving Therapy on disability.

Exploratory Aim 3: To determine the effect of Problem-Solving Therapy on other symptoms of GWI. Problem-Solving Therapy may help GWV with GWI better compensate for other symptoms (e.g. avoid over exertion) which may improve other symptoms of GWI.

Exploratory H3a – H3b Among Veterans with GWI, telephone delivered Problem-Solving Therapy will produce greater improvement in (H3a) self-reported pain and (H3b) fatigue as compared to telephone delivered health education.

Study Population

We will screen up to 2,000 Veterans to obtain a final sample of up to 300 Veterans from the Gulf War who screen positive for GWI.

Inclusion:

- (a) deployed to first Gulf War and meets Kansas definition for GWI (see definition in measures section);
- (b) scores at least a half a standard deviation worse than the mean on the World Health Organization Disability Schedule (WHO-DAS II).

Exclusion:

- (a) current suicidal/homicide intent or plan assessed by The Columbia Suicide Severity Rating Scale, schizophrenia or current psychotic symptoms
- (b) self-reported diagnosis of a degenerative brain disorder or serious psychiatric or medical illness which may limit generalizability of the findings, limit safety or account for the symptoms of GWI.

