- van der Zee, C. H., Priesterbach, A. R., van der, D. L., Kap, A., Schepers, V. P., Visser-Meily, J. M. et al. (2010). Reproducibility of three self-report participation measures: The ICF Measure of Participation and Activities Screener, the Participation Scale, and the Utrecht Scale for Evaluation of Rehabilitation-Participation. *J.Rehabil.Med.*, 42, 752-757.
- Ware, J., Jr., Kosinski, M., & Keller, S. D. (1996). A 12-Item Short-Form Health Survey: construction of scales and preliminary tests of reliability and validity. *Med.Care*, 34, 220-233.

Summary List of Measures and Timeline

Domain	Study Instruments	# of Items	Screening	Baseline	4 week	12 week	24 week (6 month)
Screening	General Screening Questionnaire	27	X				
	Columbia Suicide Severity Rating Scale [C-SSRS]	26	X			X	
	Mini International Neuropsychiatric Interview [MINI]	23	X				
	World Health Organization Disability Assessment Schedule- 12 items [WHO-DAS]	12	X				
Estimated Completion Time for Screening Domain: 35-45 minutes							
Problem-Solving	Problem Solving Inventory [PSI]	32		X	X	X	X
	Behavioral Responses to Illness Questionnaire [BRIQ]	19		X	X	X	X
Estimated Completion Time for Problem-Solving Domain: 9 minutes							
Gulf War Illness	Fatigue Severity Scale [FSS]	9		X		X	X
	KANSAS Questionnaire [KANSAS]	29	X			X	
	Patient Health Questionnaire 15-items [PHQ-15]	15		X	X	X	X
	Pain Disability Inventory [PDI] & Pain Inventory [MPI]	10		X		X	X
	MOS Sleep Scale [MOS-Sleep] & Insomnia Severity Index [ISI]	19		X		X	
Estimated Completion Time for Gulf War Illness Domain: 16 minutes							
Disability	World Health Organization Disability Assessment Schedule- 36 items [WHO-DAS]	36		X	X	X	X
	Veterans RAND 12 Item Health Survey [VR-12]	12		X		X	
	USER-P (activity satisfaction and frequency) [USER-P]	21		X		X	X
	MOS Social Support [MOS-SS]	8		X		X	X
Estimated Completion Time for Disability Domain: 14 minutes							
Participant Characterization	Alcohol Use Disorders Identification Test Alcohol Consumption Questions [AUDIT-C]	4		X		X	
	Post Traumatic Stress Disorder Checklist [PCL-5]	20		X		X	X
	Patient Health Questionnaire 8 items [PHQ-8]	9		X		X	X
	Brief Traumatic Brain Injury [BTBIS]	4		X			
	Demographics [Demo]	30		X		X	X
	Healthcare Access [HCA]	17		X		X	X
Estimated Completion Time for Characterization Domain: 12 minutes							
Veterans Perceptions of Problem-Solving and Health Education	Working Alliance Inventory (Self) [WAI]	12			X	X	
	Target Complaints Questionnaire [GOALS]	6		X		X	

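### H1 does not use the baseline 36-item and screening 12-item WHO-DAS scores as predictors of the post score, which costs some precision but causes no bias

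*Combined protocol and SAP*

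**What the plan says.** **Screening score.** Study Population admits a Veteran who "scores at least a half a standard deviation worse than the mean on the World Health Organization Disability Schedule". Assessment Instruments, a. Screening, item 2, says which form is used: "We will use the WHO-DAS 2.0 screener which is a 12 item measure at screening". It adds: "The WHO-DAS 2.0 screener explains 86% of the variance in the full measure". Screening comes first: "If a Veteran is screened as eligible to participate in the study, a date and time will be scheduled" for consent and baseline (Methods, a. Recruitment and Screening). The Summary List of Measures and Timeline marks the 12-item form at screening only.

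**Outcome.** The same item states: "As the WHO-DAS is the primary outcome measure, we will use the full, and more valid, 36 item measure during the study". The Summary List places the 36-item form at baseline and at 4, 12 and 24 weeks.

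**H1 model.** Data Analysis, a. Data, takes WHO-DAS scores as the dependent variable, with "treatment assignment [PST vs. Health education], time [pre- vs. post-intervention] and their interaction will be modeled as fixed effects". H1 is tested by the interaction. On covariates: "Variables such as age, gender, education and the confounders identified in the preliminary analysis will be controlled as covariates in the statistical analyses". The confounders to be examined in particular are depression and PTSD symptoms, and the stated ground for choosing them is a difference at baseline.

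**The concern.** Every Veteran randomised under the entry rules should have two WHO-DAS readings that precede treatment, normally from different days. Each carries day-to-day noise, so together they should predict the post score better than either alone. The stated model uses neither in that way. The baseline score is a response row, and the screening score has no place in the analysis.

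What is at stake is the precision of the primary comparison. The protocol gives up to 300 Veterans with no power, effect size, SD or dropout rate, so a reader cannot tell how much margin there is. Leaving the two scores out does not bias the treatment effect.

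**Working it through.** The plan states no precision or power figure, so there is none to reproduce.

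**Inputs.**
- From the protocol: the 12-item form explains 86% of the variance of the full form, so the correlation is √0.86 = 0.927 (taken as same-day); entry at half an SD worse than the mean; N up to 300.
- Assumed: baseline-to-post correlation *r* of 0.5 to 0.8, unit variances, normal scores, complete data, no therapist clustering.

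**Scenarios.** ρ₁ is the screener-to-baseline correlation and ρ₂ the screener-to-post correlation.
- A, equal correlations: ρ₁ = ρ₂ = 0.927*r*.
- B, screening close to baseline: ρ₁ = 0.927 × 0.9; ρ₂ = 0.927*r*.
- C, correlation decaying with time: ρ₁ = 0.927(*r* + 0.1); ρ₂ = 0.927(*r* − 0.05).

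**Truncation.** With selection at +0.5 SD, λ = φ(0.5)/(1 − Φ(0.5)) = 1.141. The screener's variance becomes v = 1 − λ(λ − 0.5) = 0.268. Then
- Var(pre) = 1 − ρ₁²(1 − v)
- Var(post) = 1 − ρ₂²(1 − v)
- Cov(pre, post) = r − ρ₁ρ₂(1 − v)

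**Variances compared.**
1. Stated contrast (complete data): Var(pre) + Var(post) − 2Cov.
2. Stated contrast plus screener-by-time: (1) − (ρ₂ − ρ₁)²v.
3. Baseline-adjusted: Var(post) − Cov²/Var(pre).
4. Baseline-adjusted plus screener: 1 − (r² + ρ₂² − 2rρ₁ρ₂)/(1 − ρ₁²).

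Example, scenario A with r = 0.6: ρ₁ = ρ₂ = 0.556, each variance 0.7735, covariance 0.3735.
- (1) 2 × (0.7735 − 0.3735) = 0.800
- (3) 0.7735 − 0.3735²/0.7735 = 0.593
- (4) 1 − (0.36 + 0.3096 − 0.3715)/0.6904 = 0.568

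Extra Veterans = 300 × ((3)/(4) − 1), from unrounded values.

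| Scenario | r | (1) | (2) | (3), cut from (1) | (4), further cut; extra Veterans | Total cut |
|---|---|---|---|---|---|---|
| A | 0.5 | 1.000 | 1.000 | 0.703, 29.7% | 0.682, 3.1%; 9.6 | 31.8% |
| A | 0.6 | 0.800 | 0.800 | 0.593, 25.9% | 0.568, 4.2%; 13.1 | 29.0% |
| A | 0.7 | 0.600 | 0.600 | 0.470, 21.7% | 0.444, 5.4%; 17.2 | 25.9% |
| A | 0.8 | 0.400 | 0.400 | 0.333, 16.7% | 0.311, 6.6%; 21.2 | 22.2% |
| B | 0.5 | 0.899 | 0.862 | 0.747, 17.0% | 0.743, 0.5%; 1.6 | 17.4% |
| B | 0.8 | 0.394 | 0.391 | 0.352, 10.6% | 0.342, 2.8%; 8.7 | 13.2% |
| C | 0.5 | 0.986 | 0.981 | 0.732, 25.8% | 0.722, 1.3%; 4.0 | 26.8% |
| C | 0.8 | 0.386 | 0.381 | 0.359, 7.0% | 0.357, 0.4%; 1.2 | 7.4% |

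**Without truncation** (v = 1), scenario A. The screener's further cut is 9.1% at r = 0.5 (0.750 to 0.682) and 13.6% at r = 0.8 (0.360 to 0.311). That is worth 300 × (0.750/0.682 − 1) ≈ 30 and 300 × (0.360/0.311 − 1) ≈ 47 Veterans. Only here, at r = 0.8, does the screener contribute slightly more than the baseline adjustment, which by itself cuts 10.0%.

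**Form of the term.** One simulated trial (N = 300, scenario A, r = 0.6, no truncation) was fitted each way. The standard error of the interaction was 0.1030 under the stated model, 0.1030 with the screener as a main effect, and 0.1032 with screener-by-time. On the same data, the baseline-adjusted model gave 0.0908 without the screener and 0.0853 with it.

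**The case against.** The strongest reply is that the screener by itself recovers little or nothing in the model the plan states. This stands. A reader might infer that the H1 analysis as written discards 10 to 20 Veterans' worth of information by omitting the screener. It does not: a main effect gains 0%, and under equal correlations so does screener-by-time. The 3% to 7% from the screener arises only once H1 is adjusted for the 36-item baseline, which is the larger change.

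Three further points stand in part.
- Nearly every input is assumed. Screening leads straight to a scheduled baseline visit, while the post score follows 12 weekly sessions, so scenarios B and C are at least as plausible as A. If the screener tells nothing beyond baseline (ρ₂ = rρ₁), its added gain is nil.
- Screening is usually by telephone, whereas baseline questionnaires are usually completed in writing at a visit. This may lower the 0.927.
- The covariate list is open-ended. A reader might infer that the screening score is excluded; the text only leaves it unassigned. But the stated entry route is baseline difference, not prognostic value, and an ordinary covariate would not help anyway.

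That other baseline measures could also be proposed is true, but these two are readings of the primary outcome itself. Nor do the documents support calling H1 biased or the trial underpowered: no power claim is made that could fail.

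**Conclusion.** The point holds as a modest, optional gain in efficiency. Two earlier readings of the primary outcome are available and neither is used to predict the post score. Using both would cut the variance of the H1 effect by about 7% to 32% against the stated contrast. With truncation at +0.5 SD, most of this comes from the 36-item baseline, and the screener adds 0.4% to 7% (about 1 to 21 Veterans on 300). Without truncation the screener's share can reach about 14%.

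These sizes rest on assumed correlations of 0.5 to 0.8, normal scores, complete data and no therapist clustering. The protocol does not say which population's mean defines eligibility. If it is a general-population norm, truncation is milder and the figures move toward the untruncated ones. The order of the protocol's sections implies that randomisation follows baseline, but this is not stated outright.

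**What to change.** In Data Analysis, a. Data, restate H1 in one of two forms:
- a model of the post-intervention 36-item WHO-DAS on treatment, with the baseline 36-item score and the screening 12-item score as covariates; or
- a mixed model with the arms constrained to a common baseline mean, the screening score having its own coefficient at each visit. This form keeps the planned within-arm improvement contrasts and uses Veterans who have a baseline but no post score.

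Keep the therapist random effect. Name both scores in advance, whether or not they differ between arms, and enter them separately; the 12- and 36-item scores should not be pooled without a scoring rule. State that both are completed before randomisation. Do not simply add the screener to the present covariate list.

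The cost is a changed model statement and one or two degrees of freedom. No new data or visits are needed.
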